1. Full title of project:

HTA commissioned call (17/19): First trimester detailed ultrasound scan for the earlier detection of fetal anomalies: Clinical and/or cost-effectiveness of first trimester ultrasound screening for fetal anomalies: Is a prospective study an efficient investment?

2. Summary of Research:

Screening for fetal anomalies is routinely performed in the second trimester at 18-21 weeks of gestation. Recent data, including a meta-analysis by our group, suggest that screening for fetal anomalies in the first trimester is feasible, and will detect just over half of all prenatally detected anomalies (1). We have also shown a significant association between the sensitivity of first-trimester ultrasound and the use of an anatomical protocol for screening.

These findings suggest that first trimester anomaly screening has the potential to be a valuable addition to prenatal care for all women. The aims of the project relate to screening for fetal anomalies in the first trimester using detailed ultrasound scanning:

1. To conduct a series of systematic reviews to inform protocol development: in particular to answer what anatomical protocol should be used; at what gestational age; using which method of scanning; what false positive rates are.
2. To undertake a survey of the current screening environment and impact on the National Institute for Health and Care Excellence (NICE) care pathway: we have identified four pathways of first trimester ultrasound used in the UK today and this nationwide survey of all maternity units will establish current practice; the choice of screening that women are offered; and what impact a suspected abnormality has in changing a woman's care from the standard NICE antenatal care pathway.
3. To perform an analysis of UK-based data currently held by the National Congenital Anomalies Disease Registry (NCARDRS – operating under the aegis of Public Health England) in order to determine whether UK NHS trusts currently performing a routine first trimester anomaly scan are able to provide their patients with an earlier diagnosis than those trusts which do not offer this service, what system factors are associated to allow this, and whether this has any impact on patient outcomes such as earlier timing of diagnostic genetic testing and earlier termination of pregnancy. As this will require special permissions and contracts with Public Health England, which can be time consuming, we will start this work as soon as possible.
4. To conduct a Delphi consensus procedure to develop a protocol for the technical and logistical aspects of first trimester anomaly screening: this will involve healthcare providers from across the UK including sonographers, midwives, obstetricians and fetal medicine experts.
5. To determine the acceptability of the early anomaly scan amongst women, partners and caregivers across the UK. This will include understanding the opinions of parents who are currently pregnant and also those who have had previous experiences of a pregnancy or child affected by a fetal congenital anomaly.
6. To conduct an economic analysis and value of information (VoI) study: we will develop a decision analytic model to estimate the expected costs and outcomes associated with current practice and with prospective first trimester anomaly screening protocols identified by the work described above. (It should be noted that as part of this we also planned a detailed scoping exercise with data held by the British Associations of Paediatric Surgeons on longer term healthcare for newborns with conditions requiring surgical correction; however, this was unable to yield economic data for ultimate use in the HE model). The model will be structured and populated using evidence from the systematic reviews; national survey; consensus procedure; and from supplementary reviews of the literature and expert elicitation as required. The model will identify the protocol most likely to be cost-effective and will be operationalised so as to facilitate a VoI analysis to determine if it is worth investing additional research resources and effort in a definitive randomised trial.
7. To draw together the findings and recommendations from the project, and, if appropriate, outline the design of plausible prospective studies or trials. The design aspects of plausible prospective studies will include population, outcome and sample size.

3. Background and Rationale:

Fetal congenital abnormalities occur in 2-5% of the fetal population (2, 3). The precise number is difficult to estimate as this value can only be based on live births and stillbirths that have undergone autopsy. As the overwhelming majority of fetuses that miscarry are not examined, the true prevalence of fetal structural abnormalities is impossible to determine. Amongst liveborn and stillborn infants and fetuses that underwent pregnancy termination, data from the European Surveillance of Congenital Anomalies register (EUROCAT) suggests a prevalence rate of 203.35 non-chromosomal anomalies per 10,000 births (95% C.I.: 201.73-204.98) (4).

Congenital anomalies represent a significant cause of fetal, neonatal, childhood and adult morbidity and mortality. In the UK (as in most developed countries) prenatal diagnosis of congenital anomalies is offered. Women in the UK are offered two routine ultrasound scans, as recommended by the National Screening Committee under the aegis of the NHS Fetal Anomaly Screening Programme (FASP) (5, 6).

The primary aims of the first (at 11-14 weeks of gestation) are to confirm viability; establish accurate gestational age from the measurement of fetal crown-rump length (CRL); identify multiple pregnancies (and in these determine chorionicity); and measure fetal nuchal translucency (NT) thickness, as part of the "Combined Screening test" (6, 7). This combines maternal age, serum free BHCG, PAPP-A and fetal NT in order to determine fetal risks for Trisomies 21,18 and 13; it offers a detection rate of approximately 85-90% for Down's Syndrome and other aneuploidies, with a false positive rate of 5% (8).

The second scan at 18-21 weeks of gestation aims mainly to detect congenital abnormalities and specifically anencephaly; open spina bifida; cleft lip; diaphragmatic hernia; gastroschisis; exomphalos; serious cardiac anomalies; bilateral renal agenesis; lethal skeletal dysplasia and chromosomal anomalies (mainly Trisomy 18 and 13) (5).

Thus, anomaly detection is currently based on this second trimester anomaly scan. The national screening program is regulated by the National Screening Committee (UK NSC) and the NHS FASP. According to NICE (6), the goals are to identify lethal and major abnormalities causing disability or those, which may be amenable to intrauterine or postnatal therapeutic management (5). The option of pregnancy termination for major fetal anomalies is enshrined in UK law (9). After mid-gestation diagnosis of anomalies this involves medical induction of labour, with a fetocide procedure recommended when the gestational age exceeds 21 weeks. Many parents who reach the difficult decision of pregnancy termination due to a major fetal anomaly feel there are potential advantages to first trimester (surgical) pregnancy termination in terms of reduced psychological morbidity (10, 11).

So is earlier detection of anomalies feasible? Considerable advancements in ultrasound technology in image quality, resolution and signal processing have fuelled interest in this field; given that the majority of fetal organ development is complete by 10 weeks gestation, ultrasound has the potential to be a valuable tool for early fetal structural anomaly screening. While studies have shown that a significant proportion of major anomalies can be detected between 11-14 weeks of gestation in both low-risk and high-risk populations (1, 12-14), there are areas of uncertainty and also potential risks, in particular in relation to false positive diagnoses. There remains some controversy as to whether first trimester anomaly screening is a sensitive enough tool to be valuable for use in daily clinical practice. In addition, unlike the current second trimester anomaly scan, there remains little international consensus as to what should be included in this early anomaly screening, in terms of both the anatomical structures which should be visualized at this stage and the image views which should be obtained for effective screening. Moreover, the specific objectives and role of first trimester anomaly screening as a part of prenatal care, particularly in relation to its second trimester counterpart, also remain unclear. This is a critical point if the health care system is expected to fund first trimester anomaly screening as part of routine practice.

4. Evidence explaining why this research is needed now:

The landscape of ultrasound in the first trimester of pregnancy in screening for anomalies is described above. Evidence why this research is needed now includes changes in clinical practice and research findings. These suggest that the detection rates are now high enough to justify assessing the utility of such a screening

approach. In addition there are parental and societal concerns about the late diagnosis of fetal abnormalities (15-17); these have increased the focus in this area, including parliamentary questions relating to late pregnancy termination(18-20).

The increasing evidence supporting the feasibility of detecting fetal structural abnormalities in the first trimester means that some - but not all - NHS hospitals have been undertaking ultrasound for detailed anatomical assessment in the first trimester and so there is lack of equity and access to care around the country. In addition, private providers offer such ultrasound scans and when problems are identified attendance in the NHS for the subsequent management of findings is common.

There is, therefore, ad hoc screening at present with very little evidence regarding the balance of risks and benefits. At the same time there are a number of uncertainties around how and when to screen; what false positive rates are; how to manage the findings; and questions about the cost, feasibility and acceptability.

In the light of these uncertainties, literature reviews and consensus, including with experts in fetal screening, and cost analyses are required. Hence the primary aim of the current proposal is for a detailed, reasoned and quantitative assessment of the potential for benefit and harm in relation to early anomaly screening using ultrasound; and how future studies should be designed to explore this.

5. Aims and objectives:

The aims and objectives have been designed to respond to the commissioning brief.

Specific aims are aligned with the work packages described below:

Aim 1 : To conduct a series of systematic reviews to inform the protocol development

- 1.1 What anatomical protocol should be used?
- 1.2 What is the best gestational age to screen?
- 1.3 Is there a preferred method of scanning (transabdominal (TA) / transvaginal (TV))?
- 1.4 What specific anomalies are amenable to first trimester detection and what are the expected detection rates?
- 1.5 What are the false positive rates for these different conditions?
- 1.6 How should data on fetal abnormalities be reported or “counted”?

Aim 2: To understand the current screening environment and impact on NICE care pathways of first trimester anomaly screening

We will conduct a nationwide survey of all maternity units to establish screening protocols; where screening takes place (hospital, primary care, etc); whether first-trimester anatomy scanning is offered irrespective of choice for aneuploidy screening; and the impact of a suspected abnormality (change from the NICE antenatal care pathway).

Aim 3: To perform an analysis of UK-based data currently held by the National Congenital Anomalies Disease Registry

The National Congenital Anomaly and Rare Disease Registration Service (NCARDRS) collects data on congenital abnormalities and rare diseases, under the aegis of Public Health England (PHE). As part of their role, NCARDRS collects information regarding the prevalence, timing of diagnosis, and outcome of fetal anomaly diagnoses of affected pregnancies across England (reporting to NCARDRS is a requirement for all trusts in England since 2017). We will request access to this data and perform an analysis to determine how the screening protocols followed by individual NHS trusts across England (ascertained in aim 2/WP 2) impact the timing of fetal congenital anomaly diagnosis, fetal genetic testing and termination of pregnancy in England.

Aim 4: To develop a protocol for the first trimester scan using a consensus procedure.

This will be based on recommended methodology, devised by experts in the field and lay representatives, including determining the acceptability of the early anomaly scan. Once the protocol is defined, we will propose auditable standards and quality assurance measures for first trimester anomaly screening.

Aim 5. Understanding parental opinions around first trimester anomaly screening

This will involve use of a validated questionnaire to understand parental attitudes around anomaly screening and to understand the acceptability of a first trimester anomaly screening programme to both parents who are currently pregnant and considered at low-risk for fetal anomalies and to parents with previous experiences of fetal anomalies in pregnancy.

Aim 6. Economic and VOI analysis

4.1 Using outputs from Aims 1, 2 and 3 we will develop an economic model to simulate and compare the costs and outcomes of the proposed protocols for first trimester fetal anomaly screening, with those of current practice. Incremental analysis will be used to explore the cost-effectiveness of protocols being compared.

4.2 The economic model will be probabilistic to facilitate VOI analysis. We will calculate the expected value of perfect information (EVPI) and partial perfect information (EVPPI) to determine whether there is economic value in undertaking additional future research. If findings are positive, we will explore the expected value of sample information (EVS), expected costs, and the expected net gain of sampling (ENG) for various trial designs and sample sizes.

Aim 7: To determine the final study design (if appropriate).

This will include designing plausible prospective studies and re-running the VOI analysis to predict the expected net gain of sampling (ENG). Where appropriate, this will include identification of the most efficient sample size for such studies, the range of sample sizes yielding a positive ENG, and comparison with the sample size yielded from a traditional power calculation.

6. Research Plan:

The background and other details are given above. This section describes the proposed work packages:

WP 1: Conducting a series of systematic reviews to inform the protocol development

All reviews will use the approach of the Cochrane Collaboration's Handbook for Diagnostic Test Accuracy Reviews [<http://srdta.cochrane.org/handbook-dta-reviews>]. The search strategy will be broadly similar to a recent systematic review and meta-analysis conducted by the lead applicants (1). With support from professional information specialist ([name]), we will search on-line databases, including, but not limited to, Medline, Embase, CINAHL, Cochrane & Web of Science. Searches will be conducted using both MeSH terms and key words (with appropriate truncations to allow variants, e.g. ultraso* to cover ultrasound, ultrasonic, ultrasonographic etc). We will also use citations of key studies, and review reference lists of relevant papers. Titles and abstracts of all papers will be reviewed by two researchers. Candidate articles will be identified and a full copy obtained and reviewed; relevant translations will be obtained by overseas colleagues where feasible, or translation services available at Oxford.

The internal validity of studies will be assessed using the QUADAS-2 tool (21); in relation to bias, sensitivity analyses, based on stratification by study quality, will then be undertaken to assess the results in sub-groups of higher quality studies. We plan to use a range of approaches for the meta-analysis. We will use the 2x2 tables from each study and assess diagnostic odds ratios (these are widely used and have some useful properties, in particular that they are the ratio of the positive and the negative likelihood ratios). A bivariate regression approach will be used to arrive at summary estimates of sensitivity and specificity. We will also use the closely related hierarchical methods to generate summary ROC curves.

Results will be pooled using a random effects meta-analysis model, due to likely heterogeneity between studies. Formal testing for heterogeneity in the meta-analysis will be undertaken and if there is evidence of significant heterogeneity, the causes will be explored using meta-regression. Heterogeneity will be quantified

using I2 and causes of heterogeneity will be explored using meta-regression, with study design characteristics as the independent variable and deviation from the summary odds ratio as the dependent variable. Publication bias will be assessed by quantitative assessment of funnel plot asymmetry. In addition, screening performance will be assessed using positive and negative likelihood ratios, sensitivity and specificity, and positive and negative predictive values.

Using this methodology we will answer the following questions

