1.5 What are the false positive rates for these different conditions?

It must be highlighted that the majority of existing studies do not report false positive rates. One of the inevitable consequences of first trimester screening is the offer of early termination of pregnancy when major anomalies are seen. There is a self-evident concern regarding offering termination of pregnancy after first trimester anomaly screening without a full understanding of a false positive diagnosis. It is not always easy to work out what a false positive is, as anomalies evolve: for example, a significant proportion of megacystis or bowel-only exomphalos resolve spontaneously with advancing gestation. Hence, it is critical not only to understand the false positive rate in first trimester screening, but also what types of anomalies are most likely to resolve spontaneously.

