We hypothesise that earlier detection of a major anomaly could alter women's preferences for continuing a pregnancy and so will construct our model to simulate the impact on the pregnancy termination rate and the number of babies born with a major anomaly. An increased risk of miscarriage from invasive testing following a false positive early screen will also be considered. Equally important is the impact on parents. The psychological sequelae of terminating a pregnancy for a major anomaly are significant and any additional burden should be reflected (10, 11, 55, 56). Furthermore, the potential for false positive results with early screening and the associated anxiety and morbidity from additional invasive testing must also be considered. In contrast, earlier anomaly detection and intervention may avert some of the distress, and may avoid the additional pressures that parents feel to reach a decision about their pregnancy before the 24-week legal termination limit (55). Also, and should a termination be chosen, an earlier procedure may expose women to less physical harm than a later procedure. We plan to explore the likely net impact of all of these consequences upon maternal and parental utility during the pregnancy.

We foresee a need to compare variants of protocols (with different anatomical specifications / screening modalities and personnel / interventional pathways) and expect to operationalise these as alternative comparators within a decision tree model covering each of the three trimesters to birth. Within each trimester, the model will be structured for any anomaly screening results, related prevalence and sensitivity/specificity and intervention pathways, and will be populated with data on associated event

probabilities, costs, and parental and infant payoffs. Separate outcomes will be presented using the decision tree and will include births with a major anomaly, and maternal and parental utility during the pregnancy (expressed as quality adjusted life years (QALYs)). At this stage, we anticipate a paucity of data on the false positive rate (and hence specificity) of tests. The statistics will also vary by anomaly. Where data are not forthcoming we will seek expert opinion using a structured elicitation technique (e.g. SHELF) (57).

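### The named routes to summary sensitivity and to exploring heterogeneity both need false-positive counts, which the protocol says most studies do not report

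*Protocol*

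**What the plan says.** Section 6, WP 1 sets one methodology for questions 1.1 to 1.6. It opens with "We plan to use a range of approaches for the meta-analysis" and continues: "We will use the 2x2 tables from each study and assess diagnostic odds ratios". For the summary estimates, "A bivariate regression approach will be used to arrive at summary estimates of sensitivity and specificity", and then "We will also use the closely related hierarchical methods to generate summary ROC curves". Pooling is by random effects. Heterogeneity is to be explored by meta-regression, "with study design characteristics as the independent variable and deviation from the summary odds ratio as the dependent variable"; no other meta-regression outcome is named. Likelihood ratios, sensitivity, specificity and predictive values are listed as further measures of performance.

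Under question 1.5 the protocol warns that "the majority of existing studies do not report false positive rates". The economic section (WP 4, 4.1) says the same of its own inputs: "At this stage, we anticipate a paucity of data on the false positive rate (and hence specificity) of tests". It offers structured expert elicitation where data are lacking. Section 13 (Data collection) says that study authors will be contacted when data cannot be extracted from the publication. No section says how a study that still lacks a false-positive count enters the meta-analysis.

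**The concern.** The protocol chooses methods that use all four cells of the 2x2 table, then reports that one of those cells is missing from most of the literature. Applied as described, the bivariate model and the odds-ratio meta-regression can use only studies with complete tables. Three things are at stake.

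- **Precision.** Sensitivity would be estimated from a minority of the studies that measured it.
- **Selection.** Studies that report false positives may differ from the rest in design, setting or follow-up. The direction of any resulting bias in sensitivity is unknown.
- **Heterogeneity.** The group's own key result under question 1.1 is an association between use of an anatomical protocol and sensitivity, and question 1.3 plans to compare sensitivities by scanning route. Neither needs false positives, but the meta-regression outcome as defined cannot be computed without them.

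WP 1 feeds the decision model, and through it the value of information analysis. The example specification in WP 4, 4.2 makes undesirable outcomes depend only on the screening test's false-positive and false-negative rates.

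**Working it through.** **Step 1: what each named analysis needs.** TP, FP, FN and TN are the four cells of a study's table.

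| Analysis in WP 1 | Quantity | Cells needed |
|---|---|---|
| Diagnostic odds ratio | (TP × TN) / (FP × FN) | all four |
| Bivariate model | TP/(TP+FN) jointly with TN/(TN+FP) | all four |
| Summary ROC | same pair | all four |
| Meta-regression as defined | study odds ratio against the summary odds ratio | all four |
| Sensitivity alone | TP/(TP+FN) | TP and FN only |

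A study that reports detected and missed anomalies, but not false positives, supports only the last row. That row has no pooling model of its own in the protocol; summary sensitivity is assigned to the bivariate model.

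**Step 2: how many studies are affected.** The protocol says a majority and gives no share. Applied to the 19 studies of the group's previous meta-analysis (question 1.1), a majority without false positives means at least 10, so at most 19 − 10 = 9 have full tables. That these 19 are typical of the literature is an assumption.

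**Step 3: illustrative loss of precision.** The quoted sensitivity for major anomalies in unselected populations is 46.10% (95% CI 36.88 to 55.46%).

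- Half-width with 19 studies: (55.46 − 36.88)/2 = 9.29 points.
- With k studies of similar weight and unchanged between-study variance, the half-width scales by √(19/k).

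| Assumed share without false positives | k with full tables | √(19/k) | Half-width (points) |
|---|---|---|---|
| just over 50% | 9 | 1.45 | 13.5 |
| 60% | about 8 | 1.54 | 14.3 |
| 75% | about 5 | 1.95 | 18.1 |

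Only the 19 studies and the interval come from the protocol. The shares, the equal weights and the constant variance are assumed. The table measures lost precision; it says nothing about bias from selection.

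**Step 4: whether the stated remedies close the gap.** Author contact could complete some tables, but its yield is unknown. Question 1.5 adds that a false positive is hard to define, because some anomalies resolve as pregnancy advances. Elicitation is placed in the economic section and supplies values for the decision model. It adds no studies to the meta-analysis.

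**The case against.** The best defence is that the protocol leaves room. It speaks of a range of approaches, lists sensitivity among the measures to be assessed, describes the evidence base in Section 8 as studies of detection rates, and reports that the group has already pooled sensitivity from 19 studies. Pooling detected and missed anomalies from all studies would be compatible with that text. Author contact is a real remedy for incomplete tables, and the economic model is protected by elicitation and by entering its parameters as distributions. Modelling detail may also sit in a review protocol or analysis plan that is not shown.

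Much of this stands, and it rules out a stronger reading. A reader might infer that the protocol discards most of the evidence by design, or that it fills missing false positives with zero and so manufactures near-perfect specificity. The documents support neither. No section excludes incomplete studies, none sets an unreported count to zero, and at least one measure exists to recover the missing data. Nor do the documents suggest that an artificial specificity would pass unnoticed into the economic model, since scarce data are expected there.

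The defence does not remove the mismatch. Compatibility is not specification: the one model named for summary sensitivity is the bivariate model, and the one meta-regression outcome named is based on the odds ratio. These are stated choices, so the point does not rest on detail that a protocol may leave to a later document.

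**Conclusion.** The concern holds in a limited form. The protocol assigns summary sensitivity to a model, and the exploration of heterogeneity to an outcome, that both need false-positive counts which it says most studies lack. Unless author contact fills most of the gaps, both would rest on a selected minority of studies, while usable sensitivity data from the others would go unused.

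The size cannot be fixed from the documents. Under the assumptions shown, the half-width for sensitivity grows from about 9.3 to about 13.5 points with 9 complete studies, and further with fewer. The contradiction itself needs no such assumption; it follows from setting the WP 1 methods beside question 1.5.

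**What to change.** Amend the meta-analysis paragraphs of Section 6, WP 1:

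1. Pool sensitivity with a random-effects binomial (logit-normal) model on TP and FN from all eligible studies.
2. Run the meta-regression on logit sensitivity in place of deviation from the summary odds ratio.
3. Restrict the diagnostic odds ratio, bivariate and summary ROC analyses, and the pooled false-positive rate, to studies that report false positives or supply them on author contact. State how many there are, and that an unreported count is not treated as zero.
4. Compare sensitivity between studies that do and do not report false positives, as a check on selection.

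This needs no new data, and Section 14 already allows Stata for the more complex models. The cost is a change of wording, a little more analysis, and visibly wider uncertainty on specificity, which reflects the evidence as the protocol itself describes it.

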1.3 Is there a preferred method of scanning (transabdominal (TA) / transvaginal (TV))?

Most reported studies use a combination of TA and TV ultrasound. Findings from studies evaluating fetal organ detection suggest that optimal visualization rates are obtained with a combination of TA and TV ultrasound(42). For TA, raised BMI, fibroids or retroversion of the uterus will decrease image quality (37, 42, 48). In contrast, TV ultrasound provides much higher resolution, but has the disadvantage of limited probe manoeuvrability (48) and reduced acceptability (37, 49). A detailed comparison between sensitivities from studies using one of the three methods (TA, TV or combination of both) will be undertaken.

1.4 What specific anomalies are amenable to first trimester detection and at what detection rates?

Some conditions seem nearly always detectable in the first trimester, others never identifiable and some can be diagnosed, depending on maternal, fetal, sonographer and equipment factors (13, 14, 27, 28). Thus, first-trimester anomaly screening may need to be considered as an adjunct, as opposed to a replacement of ultrasound examination at later gestational ages. Thus expectations and future objectives for first-trimester anomaly screening must be tailored to the type of anomalies amenable to reliable detection at this gestational age. At present, the literature has little data focused on the sensitivity of ultrasound at 12 weeks of gestation for individual anomalies. This will need to be further explored in order to identify which conditions should be specifically targeted by a national first trimester anomaly screening program.

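### The only covariate model specified in WP1 has the diagnostic odds ratio as its outcome, so it cannot separate effects on sensitivity from effects on false positives

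*Protocol*

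**What the plan says.** Section 6, WP 1 sets out the meta-analysis. DORs are to be computed from each study's 2x2 table, and are favoured partly because "they are the ratio of the positive and the negative likelihood ratios". A joint model is planned as well: "A bivariate regression approach will be used to arrive at summary estimates of sensitivity and specificity". No covariates are named for it. Hierarchical summary ROC curves are also planned.

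Differences between studies go to a meta-regression, described in two consecutive sentences. The first is conditional: "if there is evidence of significant heterogeneity, the causes will be explored using meta-regression". The second, after naming I2, says that "causes of heterogeneity will be explored using meta-regression" with no condition, and defines the model: "with study design characteristics as the independent variable and deviation from the summary odds ratio as the dependent variable".

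The text then says "Using this methodology we will answer the following questions" and lists questions 1.1 to 1.6. These include the anatomical protocol (1.1), gestational age (1.2), scanning route (1.3) and, for 1.5, "What are the false positive rates for these different conditions". Subsection 1.2 plans a sensitivity analysis of screening performance by gestation. Subsection 1.3 plans a direct comparison: "A detailed comparison between sensitivities from studies using one of the three methods (TA, TV or combination of both) will be undertaken". Subsection 1.1 cites the team's earlier review, which found sensitivity associated with use of an anatomical protocol, and describes no new covariate analysis.

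**The concern.** Questions 1.1 to 1.3 ask how a feature of the scan changes its performance. Performance has two parts, and the project turns on the balance between them: more anomalies found early, against more unaffected pregnancies flagged. A regression on the DOR returns one coefficient for both. If that coefficient differs from zero, it cannot be assigned to detection or to false positives. If a feature raises both together, the coefficient can be near zero although both have moved.

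A DOR also needs all four cells of the 2x2 table. Subsection 1.5 says most existing studies report no false positive rate. Those studies carry information on sensitivity but cannot enter this regression.

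Later work needs the two quantities apart. The decision tree in WP 4 (4.1) compares protocol variants using sensitivity and specificity. The example specification for the value-of-information analysis (4.2) makes undesirable outcomes depend only on the false positive and false negative rates. A DOR coefficient supplies neither.

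**Working it through.** The protocol states no figure on this point, so there is none to reproduce. Three checks apply.

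**1. What a constant DOR can hide.** Write Se for sensitivity, Sp for specificity and f = 1 − Sp for the false positive rate. From the protocol's own definition,

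DOR = LR+/LR− = [Se/(1−Se)] × [Sp/(1−Sp)].

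With Se = 0.461 and an assumed Sp of 0.995, both forms give 170.2.

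Inputs: Se = 46.10% (95% CI 36.88% to 55.46%; 19 studies, major anomalies, unselected populations; subsection 1.1). The protocol gives no false positive rate, so f is assumed at 0.1%, 0.5% and 1.0%. The comparison value Se = 60% is illustrative.

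For a new sensitivity Se2 at the same DOR, f2 = 1/(1 + DOR/[Se2/(1−Se2)]). The odds of detection are 0.461/0.539 = 0.855 at the start and 0.60/0.40 = 1.5 at Se2 = 60%, a ratio of 1.75.

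| Assumed f at Se 46.1% | DOR | f2 at Se 60% | Ratio | f2 at Se 55.46% | Ratio |
|---|---|---|---|---|---|
| 0.1% | 854.4 | 0.175% | 1.75 | 0.146% | 1.46 |
| 0.5% | 170.2 | 0.874% | 1.75 | 0.726% | 1.45 |
| 1.0% | 84.7 | 1.741% | 1.74 | 1.449% | 1.45 |

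In the middle row, detection rises by 13.9 points and false positives go from 500 to 874 per 100,000 unaffected fetuses, while the deviation from the summary DOR does not change. The ratio hardly depends on the assumed starting rate.

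**2. How many studies could enter.** If the statement that most studies lack false positive rates applied to the 19 studies behind the 46.1% (an assumption), at most 9 would yield a DOR.

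**3. How much the heterogeneity condition matters.** No significance level is given, so 5% is assumed. With k studies of equal variance, the power of Cochran's Q is P(χ² on k−1 df > critical value × (1−I2)).

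| k | I2 = 25% | I2 = 50% | I2 = 75% |
|---|---|---|---|
| 19 | 25% | 70% | 99% |
| 6 | 14% | 35% | 74% |

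For the 19-study set, the stated half-width is (55.46 − 36.88)/2 = 9.3 points. If 1% to 2.03% of the 115,731 fetuses were affected (assumed; 1,157 to 2,349 fetuses), sampling alone would give 1.96 × √(0.461 × 0.539/n) = 2.9 to 2.0 points. Heterogeneity in sensitivity therefore looks large, and the condition would probably be met there. It could fail in a set as small as the six high-risk studies in subsection 1.1.

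**The case against.** The strongest reply is that the DOR regression is one tool among several. WP 1 promises a range of approaches and says that sensitivity, specificity, likelihood ratios and predictive values will all be assessed. The statement that the methodology answers the listed questions covers the whole section, not this regression alone. Subsection 1.3 compares sensitivities by route directly and 1.2 examines performance by gestation; neither uses the DOR or depends on a heterogeneity test. A reader might infer that WP1 as a whole cannot detect an effect of route or gestation on sensitivity. The documents do not support that.

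A reader might also infer that meta-regression happens only after a significant test. One sentence says so, the next drops the condition, and in the main data set the test would probably be significant anyway.

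The equal-DOR illustration is built to cancel. It shows what the regression can miss, not what is likely.

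The economic model does not rest on this regression alone. WP 4 expects false positive data to be scarce and plans structured expert elicitation, WP 6 adds registry data, and Section 13 provides for contacting authors. Exact covariate lists are often left to a later plan.

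All of that limits the point but does not remove it. The outcome variable is a choice the protocol has made, not a detail left open. The bivariate model is given only the task of summary estimates. The comparison in 1.3 concerns sensitivity alone, and 1.2 names no model and does not separate false positives. For false positives by protocol or by route, no analysis is stated at all.

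**Conclusion.** The concern holds for the specified meta-regression, not for WP1 as a whole. The one covariate model in the plan cannot attribute an effect to sensitivity or to false positives, and it drops studies without false positive data. The gap is plainest for the anatomical protocol: the earlier review already links it to sensitivity, so what remains open is its cost in false positives.

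The size is illustrative: about a 1.75-fold rise in false positives hidden when sensitivity goes from 46.1% to 60% at constant DOR, and about 1.45-fold at the upper confidence limit of 55.46%. This rests on assumed starting rates of 0.1% to 1.0% and on the DOR being held exactly constant. It is not a forecast that the real coefficient will be zero. The heterogeneity condition is a secondary matter of inconsistent wording, with practical effect mainly in small sets of studies. Severity: should-fix.

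**What to change.** In WP 1, replace the regression on deviation from the summary odds ratio with the following:

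- Enter protocol detail, gestational age, scanning route and risk group as covariates in the bivariate model already named, with separate coefficients for logit sensitivity and logit specificity where data allow. Take one covariate at a time if studies are few.
- Add a random-effects meta-regression of sensitivity alone for studies that report no false positives.
- Fit these as planned analyses whatever the heterogeneity test shows, and reconcile the two consecutive sentences on meta-regression accordingly.
- Keep the DOR and I2 as descriptive summaries.

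The cost is a few sentences. The extracted data are the same, and Section 14 already names Stata for meta-regression. The downside is that effects on specificity will be imprecise, or not estimable, where few studies report false positives. That should be reported as a gap in the evidence.
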